7.3.6.2 Etiologically Relevant Windows for Exposure Assessment

For most study outcomes, the analysis will include weekly exposure cohorts that are formed throughout pregnancy (i.e., approximately 40 potential weekly cohorts beginning at Week 2 through Week 40 or the latest observed week of gestation). However, analyses of spontaneous abortion and elective termination will be restricted to the Week 2-19 Cohorts, because spontaneous abortion is defined as a pregnancy loss occurring before 20 weeks' gestation, and all pregnancies that are ongoing at Week 20 will be censored in these analyses. Analyses of preterm birth will be restricted to Weeks 2-36 Cohorts, because preterm birth is defined as a livebirth occurring before 37 weeks' gestation, and analyses of ectopic pregnancy and MCMs will be restricted to Weeks 2-13 Cohorts.

Table 2 depicts the potential gestational weeks of cohort entry for each study outcome relative to the timing of outcome assessment.

Table 2 Etiologically relevant exposure windows for study outcomes

Study Outcome	Etiologically Relevant Exposure Window	Potential Cohort Entry of Pregnancy	Start of Follow-up¹	Censoring Events²
Ectopic pregnancy	First trimester	Week 2 – Week 13	Cohort entry	End of pregnancy, disenrollment from the health plan/8 weeks of no clinical activity, or the end of the study period
Elective termination	ECD through 19 weeks' gestation (19 weeks + 6 days)	Week 2 – Week 19	Cohort entry	20 weeks + 0 days, end of pregnancy, disenrollment from the health plan/8 weeks of no clinical activity, or the end of the study period
Live births	Entire pregnancy	Week 2 – Week 40	Later of cohort entry or 20 weeks + 0 days	End of pregnancy, disenrollment from the health plan/8 weeks of no clinical activity, or the end of the study period
Preterm birth	ECD through 36 weeks' gestation (36 weeks + 6 days)	Week 2 – Week 36	Later of cohort entry or 20 weeks + 0 days	37 weeks + 0 days, end of pregnancy, disenrollment from the health plan/8 weeks of no clinical activity, or the end of the study period

Study Outcome	Etiologically Relevant Exposure Window	Potential Cohort Entry of Pregnancy	Start of Follow-up ¹	Censoring Events ²
Spontaneous abortion	ECD through 19 weeks' gestation (19 weeks + 6 days)	Week 2 – Week 19	Cohort entry	20 weeks + 0 days, end of pregnancy, disenrollment from the health plan/8 weeks of no clinical activity, or the end of the study period
Stillbirth	Entire pregnancy	Week 2 – Week 40	Later of cohort entry or 20 weeks + 0 days	End of pregnancy, disenrollment from the health plan/8 weeks of no clinical activity, or the end of the study period
MCM	First trimester	Week 2 – Week 13	Delivery	First year of life, disenrollment from the health plan/8 weeks of no clinical activity, or the end of the study period
SGA birth	Entire pregnancy	Week 2 – Week 40	Delivery	First year of life, disenrollment from the health plan/8 weeks of no clinical activity, or the end of the study period

Abbreviations: ECD, estimated conception date; EHR, electronic health record; MCM, major congenital malformation; SGA, small for gestational age

¹ For individuals with a cohort entry date after the pre-specified start of follow-up, follow-up begins at cohort entry. For example, for cohorts beginning at 24 gestational weeks, follow-up for stillbirth will begin at 24 gestational weeks.

² For EHR and linked claims-EHR data sources, pregnancies will be censored at the end of 8 weeks of no clinical activity. Since pregnant women should regularly interact with the healthcare system, this censoring criterion will indicate loss to follow-up in the database.

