7.5 Study Size

Table 3 presents the minimum number of nemolizumab exposed pregnancies required to detect relative risks equal to or greater than 2.0, 2.5, or 3.0 for a comparative analysis of each of the study outcomes, assuming a ratio of 1:4 exposed to unexposed, 80% power, a 2-sided alpha of 0.05, and the referenced outcome prevalences. For infant outcomes, the minimum number of nemolizumab-exposed livebirths was calculated, and the number of nemolizumab-exposed pregnancies was derived from these counts based on the prevalence of live birth. For the primary outcome MCM, a study size of 214 live births with linked infants exposed to nemolizumab in the first trimester exposure window would provide an 80% power to detect a RR of 2.5, and 133 live births with linked infants exposed to nemolizumab in the first trimester exposure window would provide 80% power to detect a RR of 3. Assuming 80% of pregnancies have an observed outcome and 76% of observed outcomes are live births, an estimated 352 pregnancies exposed to nemolizumab during the first trimester would need to be accrued to detect a RR of 2.5 and 219 exposed pregnancies to detect a RR of 3. With a 1:4 ratio of exposed to unexposed, this corresponds to 1,408 pregnancies (for 2.5) or 876 (for 3) in each comparator group.

Table 3 Sample size required for 80% power to detect effect estimates for pregnancy and infant outcomes, with 1:4 matching¹

Outcome	Prevalence of Outcome	Relative Risk	Nemolizumab Exposed Pregnancies Needed	Nemolizumab Exposed Live Births Needed
MCM	3% ²	2	709	431
		2.5	352	214
		3	219	133
Ectopic pregnancy	1-2%	2	877	N/A
		2.5	438	
		3	275	
Elective termination	21%	2	45	N/A
		2.5	21	
		3	12	
Preterm birth, SGA birth	10% ^{3,4}	2	190	115
		2.5	94	57
		3	56	34
Spontaneous abortion	14% ⁵	2	77	N/A
		2.5	37	
		3	22	
Stillbirth	1% ⁶	2	1,324	N/A
		2.5	662	
		3	415	

Abbreviations: N/A, not applicable; SGA, small for gestational age

¹ Calculations were performed via www.OpenEpi.com using the Fleiss method, as described in Fleiss JL. Statistical Methods for Rates and Proportions. John Wiley & Sons, 1981.

² March of Dimes. Perinatal Data Snapshot: United States Birth Defects. 2015; http://www.marchofdimes.org/peristats/pdflib/999/pds_99_4.pdf.

³ Centers for Disease Control and Prevention. Quick Stats: Percentage of Small for gestational-Age Births, by Race and Hispanic Ethnicity—United States, 2005. MMWR. 2008;57(50):1359. <https://www.cdc.gov/mmwr/preview/mmwrhtml/mm5750a5.htm>.

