7.7.3.3 Comparative Analyses

Nemolizumab-exposed pregnancies will be matched to pregnancies in the two comparator groups in a 1:4 ratio based on maternal age at cohort entry, gestational week of dispensing, indication, and calendar week, separately within each data source. For all pregnancy and infant outcomes assessed at the end of pregnancy or during pregnancy, we will estimate RRs comparing the Nemolizumab Cohort to the comparator cohorts using robust Poisson regression models (for MCMs and SGA births) and HRs using Cox proportional hazards models (for all other outcomes). All comparative analyses will be performed incorporating stabilized IPTW to adjust for potential confounding. All analyses will be conducted by data source and then meta-analyzed (as described in [Section 7.7.3.4](#)).

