11.5 Appendix E: Outcome Code Lists

Outcome	Type	Code(s)	Code Description
Ectopic Pregnancy	ICD-10-CM	O00***	Ectopic pregnancy
Ectopic Pregnancy	ICD-10 Procedure	10D27ZZ	Extraction of Products of Conception, Ectopic, Via Opening
Ectopic Pregnancy	ICD-10 Procedure	10D28ZZ	Extraction of Products of Conception, Ectopic, Endo
Ectopic Pregnancy	ICD-10 Procedure	10T20ZZ	Resection of Products of Conception, Ectopic, Open Approach
Ectopic Pregnancy	ICD-10 Procedure	10T23ZZ	Resection of Products of Conception, Ectopic, Perc Approach
Ectopic Pregnancy	ICD-10 Procedure	10T24ZZ	Resection of Ectopic POC, Perc Endo Approach
Ectopic Pregnancy	ICD-10 Procedure	10T27ZZ	Resection of Products of Conception, Ectopic, Via Opening
Ectopic Pregnancy	ICD-10 Procedure	10T28ZZ	Resection of Products of Conception, Ectopic, Endo
Ectopic Pregnancy	CPT ^{®4}	59100	Hysterotomy, abdominal (e.g., for hydatidiform mole, abortion)
Ectopic Pregnancy	CPT	59120	Surgical treatment of ectopic pregnancy; tubal or ovarian, requiring salpingectomy and/or oophorectomy, abdominal or vaginal approach
Ectopic Pregnancy	CPT	59121	Surgical treatment of ectopic pregnancy; tubal or ovarian, without salpingectomy and/or oophorectomy
Ectopic Pregnancy	CPT	59130	Surgical treatment of ectopic pregnancy; abdominal pregnancy
Ectopic Pregnancy	CPT	59135	Surgical treatment of ectopic pregnancy; interstitial, uterine pregnancy requiring total hysterectomy
Ectopic Pregnancy	CPT	59136	Surgical treatment of ectopic pregnancy; interstitial, uterine pregnancy with partial resection of uterus
Ectopic Pregnancy	CPT	59140	Surgical treatment of ectopic pregnancy; cervical, with evacuation
Ectopic Pregnancy	CPT	59150	Laparoscopic treatment of ectopic pregnancy; without salpingectomy and/or oophorectomy
Ectopic Pregnancy	CPT	59151	Laparoscopic treatment of ectopic pregnancy; with salpingectomy and/or oophorectomy
Ectopic Pregnancy	ICD-10-CM	O08**	Complications following ectopic and molar pregnancy
Elective termination	ICD-10-CM	O04**	Complications following (induced) termination of pregnancy
Elective termination	ICD-10-CM	O07**	Failed attempted termination of pregnancy
Elective termination	ICD-10-CM	Z33.2	Encounter for elective termination of pregnancy
Elective termination	ICD-10 Procedure	10A00ZZ	Abortion of Products of Conception, Open Approach
Elective termination	ICD-10 Procedure	10A03ZZ	Abortion of Products of Conception, Percutaneous approach

⁴ CPT copyright 2024 American Medical Association. All rights reserved.

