Outcome	Type	Code(s)	Code Description
Elective termination	ICD-10 Procedure	10A04ZZ	Abortion of Products of Conception, Perc Endo Approach
Elective termination	ICD-10 Procedure	10A07Z6	Abortion of Products of Conception, Vacuum, Via Opening
Elective termination	ICD-10 Procedure	10A07ZW	Abortion of Products of Conception, Laminaria, Via Opening
Elective termination	ICD-10 Procedure	10A07ZX	Abortion of POC, Abortifacient, Via Opening
Elective termination	ICD-10 Procedure	10A07ZZ	Abortion of Products of Conception, Via Opening
Elective termination	ICD-10 Procedure	10A08ZZ	Abortion of Products of Conception, Endo
Elective termination	HCPCS	S0190	Mifepristone Oral 200mg
Elective termination	HCPCS	S0191	Misoprostol, oral, 200 mcg
Elective termination	HCPCS	S0199	Medically induced abortion by oral ingestion of medication including all associated services and supplies (e.g., patient counseling, office visits, confirmation of pregnancy by HCG, ultrasound to confirm duration of pregnancy, ultrasound to confirm completion of abortion) except drugs
Elective termination	HCPCS	S2260	Induced abortion, 17-24 weeks
Elective termination	HCPCS	S2265	Induced abortion, 25-28 weeks
Elective termination	HCPCS	S2266	Induced abortion, 29-31 weeks
Elective termination	HCPCS	S2267	Induced abortion, 32 weeks/greater
Elective termination	CPT ⁵	01965	Anesthesia for incomplete or missed abortion procedures
Elective termination	CPT	01966	Anesthesia for induced abortion procedures
Elective termination	CPT	59840	Induced abortion, by dilation and curettage
Elective termination	CPT	59841	Induced abortion, by dilation and evacuation
Elective termination	CPT	59850	Induced abortion, by 1 or more intra-amniotic injections (amniocentesis-injections), including hospital admission and visits, delivery of fetus and secundines;
Elective termination	CPT	59851	Induced abortion, by 1 or more intra-amniotic injections (amniocentesis-injections), including hospital admission and visits, delivery of fetus and secundines; with dilation and curettage and/or evacuation
Elective termination	CPT	59852	Induced abortion, by 1 or more intra-amniotic injections (amniocentesis-injections), including hospital admission and visits, delivery of fetus and secundines; with hysterotomy (failed intra-amniotic injection)

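### The live-birth hazard ratio, taken from 20 weeks onwards, measures when delivery occurs rather than whether a live birth occurs; elective termination is cut at 20 weeks without a reason of its own and shares a miscarriage code

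*Protocol*

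**What the plan says.** **Live birth.** Section 7.4.2.1.3 defines it without any gestational limit, and section 6 makes its frequency an objective. Table 2 allows cohort entry from Week 2 to Week 40 but starts follow-up at the later of cohort entry or 20 weeks + 0 days. Section 7.7.3.3 reserves robust Poisson models for MCM and SGA birth and assigns "HRs using Cox proportional hazards models (for all other outcomes"), which includes live birth.

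**Elective termination.** Section 7.3.6.2 states that "analyses of spontaneous abortion and elective termination will be restricted to the Week 2-19 Cohorts, because spontaneous abortion is defined as a pregnancy loss" before 20 weeks. Table 2 and section 7.3.6.7 repeat the censoring at 20 weeks. Section 7.4.2.1.2 defines termination as an intervention that ends a pregnancy before delivery, with no upper limit. Appendix E lists four gestation-specific termination codes: S2260 (17-24 weeks), S2265 (25-28), S2266 (29-31) and S2267, "Induced abortion, 32 weeks/greater".

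**Code lists.** CPT 01965, "Anesthesia for incomplete or missed abortion procedures", stands under both elective termination and spontaneous abortion in Appendix E. The termination list also contains O07, "Failed attempted termination of pregnancy". Section 7.4.2.1.5 says that one listed code is enough for spontaneous abortion. The protocol states no rule for a pregnancy that meets both lists.

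**The concern.** A reader will take a live-birth hazard ratio above 1 as more live births, and one of 1 as no difference. Neither reading is safe here. By 20 weeks the miscarriages and earlier terminations have left the risk set, and among the remaining pregnancies almost the only thing that varies is the date of delivery. Earlier delivery, which is a harm, raises the ratio. A real fall in the proportion of live births through early loss leaves it unchanged.

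For termination, the definition, the code list and the follow-up window cannot all stand. The shared anaesthesia code lets one miscarriage count as both outcomes, and a failed attempt does not by itself show that the pregnancy ended.

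**Working it through.** **1. The plan's own figures.** Table 3 has no live-birth row. Its termination row (21% prevalence, 45 / 21 / 12 exposed pregnancies at RR 2 / 2.5 / 3) was checked with the stated inputs ("assuming a ratio of 1:4 exposed to unexposed, 80% power, a 2-sided alpha of 0.05") by the Fleiss formula without continuity correction:

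n = [1.960·√((1 + 1/4)·p̄·q̄) + 0.842·√(p₁q₁ + p₀q₀/4)]² / (p₁ − p₀)²

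At RR 2, p₀ = 0.21, p₁ = 0.42 and p̄ = (0.42 + 4 × 0.21)/5 = 0.252. Then n = (0.951 + 0.449)² / 0.0441 = 44.5, so 45. The other two entries also reproduce. The sample-size arithmetic is not at fault; the problem is what is being counted.

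**2. Live birth, timing changed and probability unchanged.** Assume 10% preterm births in the comparator, 20% in the exposed, and the same timing among births from 37 weeks.
- Before 37 weeks the ratio of cumulative hazards is −ln(0.80) / −ln(0.90) = 0.223 / 0.105 = 2.12.
- From 37 weeks the ratio is 1.
- With equal groups, about 15% of births are preterm (the mean of 10% and 20%), so the average log ratio is roughly 0.15 × ln 2.12 = 0.113, a hazard ratio of about 1.12.
- Simulation with follow-up from week 20 gives about 1.11. The risk ratio of live birth is 1.00.

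A second simulation (40,000 pregnancies per arm; delivery at 39 weeks, SD 1.8; 14% miscarriage; 1% stillbirth) shifts all deliveries earlier with the same live-birth probability. The hazard ratio is 1.28 for half a week and 1.63 for one week.

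**3. Live birth, probability changed.**

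| Change in the exposed group | Risk ratio of live birth | Hazard ratio from 20 weeks |
|---|---|---|
| Stillbirth 1% to 3% | 0.97/0.99 = 0.98 | about 1.00 |
| Miscarriage 14% to 28% | 0.72/0.86 = 0.84 | 1.00 |

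Stillbirths are censored, which leaves the hazard of live birth among ongoing pregnancies unchanged. Miscarriages never reach the start of follow-up.

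**4. Termination, truncation.** S2265, S2266 and S2267 lie wholly beyond 20 weeks, so they cannot count as termination events; S2260 straddles the cut. The share of terminations at or after 20 weeks is not in the document. If it were 1%, 5% or 10%, the exposed number at RR 2 would be 46, 48 or 52 instead of 45.

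**5. Termination, shared code.** Let f be the share of miscarriages carrying CPT 01965, also not in the document. With 21% terminations and 14% miscarriages (Table 3) and no effect on miscarriage, the observed ratio for a true ratio of 2 is (0.42 + 0.14f) / (0.21 + 0.14f):
- f = 5%: 0.427/0.217 = 1.97
- f = 10%: 1.94
- f = 25%: 1.86
- f = 50%: 0.490/0.280 = 1.75

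If termination is unaffected but miscarriage doubles, the observed termination ratio is (0.21 + 0.28f) / (0.21 + 0.14f), which is 1.03 at f = 5% and 1.25 at f = 50%.

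**The case against.** The best defence on live birth is that nothing is hidden: preterm birth, stillbirth, spontaneous abortion and termination each have their own analysis, so a harm would appear there. That stands. The defect is a ratio that is uninformative and easy to misread, not a missed safety signal.

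On termination, three replies have force. Terminations before 20 weeks are still captured. The late codes still serve a purpose: they can mark the end of pregnancy, which is a censoring event for other outcomes, and the stillbirth algorithm in section 7.4.2.1.6 looks for competing outcome codes. And a precedence rule for overlapping codes may sit in the pregnancy algorithm (section 7.2.1.1) or in an analysis plan that is not at hand. None of these supplies a reason for cutting termination at 20 weeks, or explains why a code for incomplete or missed abortion belongs in the termination list.

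Three stronger readings are tempting and are not supported:
- *Neither outcome measures what it is meant to.* This goes too far for termination, which is truncated and somewhat contaminated but still largely captured under the assumed ranges.
- *About 35% of pregnancies (21% + 14%) end before live-birth follow-up starts.* Those Table 3 prevalences should not be added, and section 7.5 itself assumes "76% of observed outcomes are live births", which leaves only 24% for all other outcomes together.
- *Late terminations are lost to the MCM bias analysis.* Section 7.7.3.5.8 does not say that its inputs are limited to the 20-week follow-up in Table 2.

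**Conclusion.** The live-birth point holds. As specified, the hazard ratio does not track the probability of live birth: it moves to about 1.11 when only preterm timing changes, and stays at about 1.00 when stillbirth triples or miscarriage doubles. The exact values depend on assumed delivery-time distributions. The direction follows from starting follow-up at 20 weeks, when nearly all remaining pregnancies will end in live birth.

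The termination points hold as secondary inconsistencies. Their effect looks modest under the assumed ranges (45 becomes 46 to 52; a true ratio of 2 is seen as 1.97 to 1.75), but neither driving share is in the document, so the real size is unknown. The primary outcome, MCM, is not directly changed. The changes should be made, because each corrects something the protocol already fixes.

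**What to change.** **Live birth.** In Table 2, start follow-up at cohort entry. In section 7.7.3.3, replace its Cox model with the proportion of live births, estimated as cumulative incidence with losses as competing events and censoring handled, and compared by a risk ratio. Censoring matters because section 7.5 assumes that only 80% of pregnancies have an observed outcome.

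**Elective termination.** In Table 2 and sections 7.3.6.2 and 7.3.6.7, follow it to the end of pregnancy. Alternatively, state and justify one gestational limit and use it in the definition, the code list and the window alike.

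**Codes.** Remove CPT 01965 from the termination list, and count O07 only with evidence that the pregnancy ended.

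**Cost.** Text edits to Table 2, the related sections and Appendix E, with no new data. The live-birth change needs a different estimator in each database, and section 7.7.3.4 must accept risk ratios with confidence intervals, since it now names hazard ratios or events and person-time as inputs.

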7.2.1.1.1 Pregnancy Identification

To identify pregnancies, Optum searches the administrative claims for combinations of diagnostic and procedure codes indicating a pregnancy, delivery, or pregnancy endpoint, as well as prenatal care. This process has been described previously by Bertoia et al. (2022). Women are required to have at least one pregnancy-related health insurance claim to be considered as having a pregnancy. The first pregnancy-related claim is identified a median of 74 days (range 1, 294; mean 114.3 [standard deviation 80.1]) after last menstrual period (LMP). If a woman has more than one eligible pregnancy during the study period, each of the qualifying pregnancies may be included. Analyses will account for the correlations between multiple pregnancies for a given woman. It should be noted that the first observed pregnancy per woman in the claims database might not be that woman's first pregnancy.

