7.3.2 Inclusion Criteria

Pregnancies among women who meet the following criteria will be eligible for inclusion in the study:

- An ECD between 12 August 2024 and 31 March 2032
- For claims data sources, continuous health plan enrollment with complete medical and pharmacy benefit coverage from 6 months before and including cohort entry (only applicable to the pregnant woman)
- For linked claims-EHR data sources:
 - Pharmacy (but not medical) coverage during the full pregnancy period (as described in [Table 1](#)) will be required to ensure dispensings of cohort defining drugs are captured. (A shorter period of continuous enrollment will be required for linked claims-EHR data sources compared with the claims databases because pharmacy claims will be used primarily for exposure assessment, while covariates will be assessed from the EHR data).
 - Presence of at least one outpatient clinical visit at least 6 months prior cohort entry (to establish a 6-month baseline period for assessment of AD and PN as well as clinical covariates).
- Evidence of moderate to severe AD or PN ascertained using appropriate algorithms

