7.3.6 Study Population

7.3.6.1 Exposure Cohorts and Cohort Entry

[figure not shown]
Based on the sequential cohort design, a series of study cohorts will be established for each gestational week of pregnancy ([Caniglia et al., 2023](#); [Hernández-Diaz S et al., 2023](#)). To ensure capture of exposure to AD/PN treatments prior to the ECD but which remain in the body at ECD, the first gestational week of pregnancy will be extended (prior to ECD) by 5 times the half-life for each AD/PN treatment. For example, since nemolizumab has a half-life of 18.9 days ([Nemluvio PI, 2025](#)), the first gestational week for nemolizumab will begin 95 days (approximately 14 weeks) prior to ECD. The half-life for each AD/PN treatment is provided in [Appendix D](#).

As nemolizumab and the comparator AD/PN treatments are injection drugs that are dispensed at a pharmacy for self-injection, treatment duration will be defined as date of dispensing plus 5 times the half-life of the therapy when a single pre-filled syringe, pen, or autoinjector is dispensed. When multiple units are dispensed, the days' supply will be calculated based on the quantity dispensed and recommended administration schedule; treatment duration will be calculated as the date of dispensing plus the days' supply plus 5 times the half-life of the therapy. A treatment will be considered to be overlapping with the first gestational week of pregnancy if there is at least one dispensing or dose received during the period 5 times the half-life prior to ECD through the end of the first gestational week. At each gestational week, we will first restrict to eligible pregnancies with no administrations or dispensings of nemolizumab or the other AD/PN treatments from 5 times the half-life of the corresponding treatment (e.g., 95 days, or approximately 14 weeks, for nemolizumab) before ECD through the end of the prior gestational week. We will then classify exposure status as exposed to nemolizumab, exposed to other AD/PN treatments, or unexposed based on the pregnancy's receipt of nemolizumab or other AD/PN treatments during that gestational week. Pregnancies among women with claims for both nemolizumab and another AD/PN treatment during the relevant exposure window will be excluded. For exposed pregnancies with more than one dose of the index treatment (e.g., two doses of nemolizumab) during pregnancy, cohort entry will align with the first dose.

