Cohort entry will be set at the date of dispensing in the Nemolizumab Cohort (i.e., the earliest nemolizumab administration date during a pregnancy) and the Other AD/PN Treatment Cohort,

and the corresponding day of gestation among unexposed pregnancies, rounded down to the nearest week. For example, for pregnancies entering the Week 8 Cohort, we will first select all pregnancies with no nemolizumab or other AD/PN treatment from 5 times the half-life before ECD through 7 weeks' + 6 days' gestation. Then, we will assign the pregnancies that receive nemolizumab during Week 8 (8 weeks + 0 days through 8 weeks + 6 days) to the nemolizumab-exposed group, those that received another AD/PN treatment to the other treatment-exposed group, and those that did not receive nemolizumab or another AD/PN treatment during Week 8 to the unexposed group. Cohort entry among the Week 8 nemolizumab and comparator cohorts will be set to 8 weeks' + 0 days. The pregnancies in the Week 8 exposed cohort will no longer be eligible for inclusion in subsequent weekly cohorts. However, the pregnancies in the Week 8 unexposed group will go on to be eligible for inclusion in the Week 9 Cohort, at which point their exposure status would be reassessed during Week 9 (9 weeks + 0 days through 9 weeks + 6 days). A pictorial depiction of this process can be found in Figure 1 and key pregnancy dates can be found in Table 1. If the study size does not permit weekly sequential cohorts, the cohorts may be collapsed into longer (e.g., 2-week, 4-week) intervals as needed.

Figure 1 Sequential cohort design, depicting an example of cohort entry for the Week 7 and Week 8 cohorts

Abbreviations: AD, atopic dermatitis; ECD, estimated conception date; PN, prurigo nodularis

Table 1 Pregnancy dates

Date	Definition
LMP	First day of last menstrual period 0 gestational weeks ^{0/7 days}
Gestational age	Weeks of gestation Anchored by LMP Number of completed weeks elapsed after LMP

Date	Definition
ECD	Estimated as LMP + 14 days 2 gestational weeks ^{0/7 days}
First trimester	Begins at ECD minus 5 times the half-life of the treatment Ends at LMP + 97 days
Second trimester	Begins at LMP + 98 days Ends at LMP + 195 days
Third trimester	Begins at LMP + 196 days Ends at pregnancy outcome
Pregnancy period	Begins at ECD minus 5 times the half-life of the treatment Ends at pregnancy outcome

Abbreviations: ECD, estimated conception date; LMP, first day of last menstrual period

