7.3.6.7 Follow-up

For each weekly cohort, pregnancies will be followed from the date after cohort entry until the earliest of the end of pregnancy, disenrollment from the health plan (for claims databases), 8 weeks with no clinical activity recorded (for the linked claims-EHR database or EHR-only databases) or the end of the study period (31 March 2032 or latest data available). Each linked infant will be followed from delivery until the earliest of end of first year of life, disenrollment from the health plan (for claims databases), 8 weeks with no clinical activity recorded (for the linked claims-EHR database or EHR-only databases) or the end of the study period. Follow-up for spontaneous abortion and elective termination will be censored at 20 weeks' gestation, and follow-up for preterm birth will be censored at 37 weeks' gestation. The censoring events for each outcome are summarized in [Table 2](#).

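### In EHR-linked sources the 8-week inactivity rule also ends infant follow-up, without a rationale, and can cut short the one-year window for the primary outcome (MCM)

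*Protocol*

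**What the plan says.** Table 2 (section 7.3.6.2) lists, as censoring events for every outcome including MCM and SGA birth, disenrollment or 8 weeks of inactivity. Footnote 2 assigns the inactivity version to EHR and linked claims-EHR sources, where "pregnancies will be censored at the end of 8 weeks of no clinical activity", and gives the reason: "Since pregnant women should regularly interact with the healthcare system, this censoring criterion will indicate loss to follow-up in the database". The footnote does not mention infants.

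Section 7.3.6.7 states the rule twice, once for pregnancies and once for children. On the latter it begins "Each linked infant will be followed from delivery until the earliest of end of first year of life" and then lists disenrollment (claims databases), 8 weeks without recorded activity (linked or EHR-only databases) and the end of the study period. The ORD, a claims database, therefore has no inactivity rule.

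Section 7.4.2.2.1 gives the purpose of the infant year: to find malformations that do not come to light at birth. What counts as clinical activity is not defined in the protocol.

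For the maternal side, section 7.2.1.1.1 reports from the ORD that "The first pregnancy-related claim is identified a median of 74 days" after LMP. The earliest cohort is Week 2, at the estimated conception date ("Estimated as LMP + 14 days"). It also takes in earlier dispensings, because "the first gestational week for nemolizumab will begin 95 days (approximately 14 weeks) prior to ECD".

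**The concern.** An inactivity rule identifies loss to follow-up only if people who are still under observation would be expected to generate a record within the gap. The protocol argues this for pregnant women and then applies the same 56 days to infants with no argument at all. MCM is the primary outcome, and the infant year exists to pick up late-recognised malformations. Those are the cases that a short gap rule discards: an infant silent for 56 days and then seen with a coded malformation has already left follow-up.

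Two things are at stake. MCM ascertainment in the linked sources could fall below what the planned year would give, which costs power. It could also differ from the ORD, and section 7.7.3.4 combines the sources by meta-analysis.

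On the maternal side, the premise of regular contact is weakest in the first weeks, before prenatal care has begun. Follow-up for ectopic pregnancy, elective termination and spontaneous abortion starts at cohort entry, so early censoring would fall on those outcomes.

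**Working it through.** **1. The plan's own size reproduces.** Section 7.5 inputs: MCM prevalence p0 = 0.03, RR 2.5 so p1 = 0.075, ratio r = 4, two-sided alpha 0.05, power 80%. Fleiss formula without continuity correction, with p̄ = (0.075 + 4 × 0.03)/5 = 0.039:

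n = [1.96 √((r+1) p̄(1−p̄)) + 0.8416 √(r p1(1−p1) + p0(1−p0))]² / [r (p1−p0)²]

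= [1.96 × 0.4329 + 0.8416 × 0.5537]² / 0.0081 ≈ 213.3, rounded up to **214**. Then 214/(0.80 × 0.76) = **352** pregnancies. Both match section 7.5, and the size is not in dispute.

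**2. What an infant needs to complete the year.** One gap above 56 days ends follow-up.
- Shortest possible follow-up: 56/365 = 15% of the year.
- 365/56 = 6.52, so at least six recorded contacts after birth are needed, with no gap above 56 days. Five contacts reach at most 6 × 56 = 336 days.
- Regular contacts every 56 days or less lose nothing.

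The protocol gives no infant visit frequency. If contacts occurred at random (an assumed Poisson process, simulated), the result would be:

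| Contacts per year (assumed) | Mean follow-up, days | Reach 365 days |
|---|---|---|
| 6 | 92 | 0.2% |
| 12 | 152 | 7% |
| 16 | 203 | 20% |
| 26 | 301 | 63% |

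The loss can thus be anything from none to most of the year.

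**3. What missed malformations would cost.** Suppose a fraction m of MCMs is missed equally in both arms, so that RR stays at 2.5, with 214 exposed and 856 comparator infants. Power is Φ(z), where

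z = [(p1−p0)√(4 × 214) − 1.96 √(5 p̄(1−p̄))] / √(4 p1(1−p1) + p0(1−p0)),

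and p0, p1 are both multiplied by (1 − m):
- m = 0: 80%
- m = 10%: 76%
- m = 20%: 72%
- m = 30%: 67%

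These figures apply the loss to all infants. If only a share s comes from affected sources, the overall loss is about s × m. With half from the ORD and m = 20% in the rest, it is 0.5 × 20% = 10%, giving about 76%. The values of m and s are assumptions.

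**4. The maternal clock.** With no recorded activity after entry, censoring falls at entry day + 56:
- Week 2: 14 + 56 = LMP + 70, 4 days before the 74-day median. At least half of pregnancies then have no pregnancy-related claim.
- Week 3: 21 + 56 = LMP + 77, already past the median.
- Week 8: LMP + 112. Week 13: LMP + 147.

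If the time to the earliest pregnancy-related claim is lognormal with the stated median 74 and mean 114.3 (an assumed shape), about 48%, 33% and 23% of pregnancies have that claim after days 77, 112 and 147.

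Week 2 is also the cohort into which pre-conception dispensings are folded: 95 + 7 = 102 days of nemolizumab dispensings, against 7 days for each later cohort.

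**The case against.** The maternal argument is open to serious objections, and most of them stand. Any recorded activity restarts the clock, not only a pregnancy-related claim, and the cohort is selected for skin-disease care by sections 7.3.4 and 7.3.5. The 74-day median is an ORD figure, and the ORD does not use this rule. Against that median only Week 2 entrants are cut, by 4 days. Live birth, preterm birth and stillbirth follow-up starts no earlier than 20 weeks, and MCM and SGA birth at delivery. A reader might infer that the rule removes early pregnancies wholesale. The documents do not support that.

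Four further inferences should also be resisted:
- *Censoring differs by arm because treated women see more care.* The protocol gives no data on this. Unexposed women meet the same disease definition and may be on other treatment, and section 7.10 plans to describe censoring by exposure status.
- *The rule contradicts the requirement for "Pharmacy (but not medical) coverage during the full pregnancy period".* It does not. That coverage is required to capture exposure, whereas EHR activity measures something else.
- *Infants lose most of the year.* This depends on a visit frequency that the protocol does not state.
- *Censored infants are counted as free of MCM.* The protocol does not say how they enter the Poisson model, a detail that an SAP may settle.

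It can also be said that malformations coded at birth are captured regardless, that the rule is the same in every arm within a source, and that the meta-analysis reports heterogeneity. All three are true. None supplies a reason for the infant rule or recovers a malformation first coded after a 56-day gap. The checks in section 7.10 describe censoring without correcting for it, and no sensitivity analysis in section 7.7.3.5 varies the gap.

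**Conclusion.** The point holds for infants. The 8-week rule is applied to them in Table 2 and section 7.3.6.7 without a rationale. It works against the one-year window of section 7.4.2.2.1 and makes infant follow-up end differently from the ORD. The direction is clear: late-detected MCMs can be lost. The size cannot be established from the protocol. The fall in power from 80% to between 76% and 67% is an illustration that assumes 10% to 30% of MCMs are missed equally in both arms and in every infant. It shrinks with the share of infants from the ORD.

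The maternal point is secondary. A Week 2 entrant with no recorded activity of any kind can be censored at LMP + 70, before prenatal care is typically visible, provided the ORD median carries over to EHR sources. This concerns ectopic pregnancy, elective termination and spontaneous abortion. It deserves attention mainly because Week 2 collects the pre-conception dispensings and because clinical activity is undefined.

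**What to change.** - **Infants, in EHR and linked sources:** remove the 8-week rule and follow to 12 months or the end of coverage or available data. Alternatively, use a materially longer gap, for example 6 months. Keep 8 weeks as a sensitivity analysis.
- **Pregnancies:** define clinical activity, stating that dispensings and linked claims count. Start the inactivity clock no earlier than the first pregnancy-related encounter.
- **Text:** amend Table 2, its footnote 2 and section 7.3.6.7 together, and give the infant rule its own justification.

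Censoring pregnancies at loss of pharmacy coverage is not a usable alternative. Section 7.3.2 already requires that coverage through the pregnancy outcome, so such a rule would never trigger.

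The cost is wording and programming before the final extract. The downside is that some infants and women truly lost from the EHR will be censored later and will contribute event-free follow-up. The 8-week sensitivity analysis would show how much this matters for infants.
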